8.3 Lost to Follow-Up

- All reasonable efforts must be made to locate participants to determine and report their ongoing status. This includes follow-up with persons authorized by the participant.
- Lost to follow-up is defined by the inability to reach the participant after a minimum of **three** documented phone calls, faxes, or emails as well as lack of response by participant to one registered mail letter. All attempts should be documented in the participant's medical records.
- If it is determined that the participant has died, the site will use permissible local methods to obtain date and cause of death.
- If investigator's use of third-party representative to assist in the follow-up portion of the study has been included in the participant's informed consent, then the investigator may use a Sponsor retained third-party representative to assist site staff with obtaining participant's contact information or other public vital status data necessary to complete the follow-up portion of the study.

Clinical Protocol
BMS-986177

CV010010
FXIa

- The site staff and representative will consult publicly available sources, such as public health registries and databases, in order to obtain updated contact information.
- If after all attempts, the participant remains lost to follow-up, then the last known alive date as determined by the investigator should be reported and documented in the participant's medical records.

9. STUDY ASSESSMENTS AND PROCEDURES

- Study procedures and timing are summarized in the Schedule of Activities.
- Protocol waivers or exemptions are not allowed.
- All immediate safety concerns must be discussed with the Sponsor immediately upon occurrence or awareness to determine if the participant should continue or discontinue treatment.
- Adherence to the study design requirements, including those specified in the Schedule of Activities, is essential and required for study conduct.
- All screening evaluations must be completed and reviewed to confirm that potential participants meet all eligibility criteria before randomization. The investigator will maintain a screening log to record details of all participants screened and to confirm eligibility or record reasons for screening failure, as applicable.
- Procedures conducted as part of the participant's routine clinical management (eg, blood count) and obtained before signing of informed consent may be utilized for screening or baseline purposes provided the procedure meets the protocol-defined criteria and has been performed within the timeframe defined in the Schedule of Activities.

9.1 Efficacy Assessments

Not Applicable

9.1.1 *Imaging Assessment for the Study*

Not Applicable

9.2 Adverse Events

The definitions of an AE or serious adverse event (SAE) can be found in [Appendix 3](#).

AEs will be reported by the participant (or, when appropriate, by a caregiver, surrogate, or the participant's legally authorized representative).

The investigator and any designees are responsible for detecting, documenting, and reporting events that meet the definition of an AE or SAE and remain responsible for following up AEs that are serious, considered related to the study treatment or the study, or that caused the participant to discontinue before completing the study.

SAE reporting specified in [Appendix 3](#)

9.2.1 *Time Period and Frequency for Collecting AE and SAE Information*

The collection of nonserious AE information should begin at initiation of study treatment until [the follow-up contact], at the timepoints specified in the Schedule of Activities ([Section 2](#)).

Clinical Protocol
BMS-986177

CV010010
FXIa

Nonserious AE information should also be collected from the start of a placebo lead-in period or other observational period intended to establish a baseline status for the participants.

Sections 5.6.1 and 5.6.2 in the Investigator Brochure (IB) represent the Reference Safety Information to determine expectedness of serious adverse events for expedited reporting. Following the participant's written consent to participate in the study, all SAEs, whether related or not related to study drug, must be collected, including those thought to be associated with protocol-specified procedures.

All SAEs must be collected that occur during the screening period and within 30 days of discontinuation of dosing.

- Medical occurrences that begin before the start of study treatment but after obtaining informed consent will be recorded on the appropriate section of the eCRF section.
- All SAEs will be recorded and reported to Sponsor or designee within 24 hours, as indicated in [Appendix 3](#).
- The investigator will submit any updated SAE data to the sponsor within 24 hours of this being available.

Investigators are not obligated to actively seek AEs or SAEs in former study participants. However, if the investigator learns of any SAE, including a death, at any time after a participant has been discharged from the study, and he/she considers the event reasonably related to the study treatment or study participation, the investigator must promptly notify the sponsor.

The method of evaluating, and assessing causality of AEs and SAEs and the procedures for completing and reporting/transmitting SAE reports are provided in [Appendix 3](#).

9.2.2 Method of Detecting AEs and SAEs

Adverse events can be spontaneously reported or elicited during open-ended questioning, examination, or evaluation of a subject. (In order to prevent reporting bias, subjects should not be questioned regarding the specific occurrence of one or more AEs.)

9.2.3 Follow-up of AEs and SAEs

- Nonserious AEs should be followed to resolution or stabilization, or reported as SAEs if they become serious (see [Appendix 3](#)).
- Follow-up is also required for nonserious AEs that cause interruption or discontinuation of study treatment and for those present at the end of study treatment as appropriate.
- All identified nonserious AEs must be recorded and described on the nonserious AE page of the CRF (paper or electronic). Completion of supplemental CRFs may be requested for AEs and/or laboratory abnormalities that are reported/identified during the course of the study.

After the initial AE/SAE report, the investigator is required to proactively follow each participant at subsequent visits/contacts. All SAEs, and non-serious AEs of special interest (as defined in [Section 9.2](#) will be followed until resolution, until the condition stabilizes, until the event is otherwise explained, or until the participant is lost to follow-up (as defined in [Section 8.3](#)).

Further information on follow-up procedures is given in [Appendix 3](#).

9.2.4 Regulatory Reporting Requirements for SAEs

- Prompt notification by the investigator to the Sponsor of SAEs is essential so that legal obligations and ethical responsibilities towards the safety of participants and the safety of a product under clinical investigation are met.
- An investigator who receives an investigator safety report describing SAEs or other specific safety information (e.g., summary or listing of SAEs) from the Sponsor will file it along with the Investigator's Brochure and will notify the IRB/IEC, if appropriate according to local requirements.

Sponsor or designee will be reporting adverse events to regulatory authorities and ethics committees according to local applicable laws including European Directive 2001/20/EC and FDA Code of Federal Regulations 21 CFR Parts 312 and 320. A SUSAR (Suspected, Unexpected Serious Adverse Reaction) is a subset of SAEs and will be reported to the appropriate regulatory authorities and investigators following local and global guidelines and requirements.

9.2.5 Pregnancy

If, following initiation of the study treatment, it is subsequently discovered that a participant is pregnant or may have been pregnant at the time of study exposure, including during at least 5 half-lives after product administration, the investigator must immediately notify the BMS Medical Monitor/designee of this event and complete and forward a Pregnancy Surveillance Form to BMS Designee within 24 hours of awareness of the event and in accordance with SAE reporting procedures described in [Appendix 3](#)

In most cases, the study treatment will be permanently discontinued in an appropriate manner (eg, dose tapering if necessary for participant safety). Please call the BMS Medical Monitor within 24 hours of awareness of the pregnancy.

Protocol-required procedures for study discontinuation and follow-up must be performed on the participant.

Any pregnancy that occurs in a female partner of a male study participant should be reported to Sponsor or designee. In order for Sponsor or designee to collect any pregnancy surveillance information from the female partner, the female partner must sign an informed consent form for disclosure of this information. Information on this pregnancy will be collected on the Pregnancy Surveillance Form.

9.2.6 Laboratory Test Result Abnormalities

The following laboratory test result abnormalities should be captured on the nonserious AE CRF page or SAE Report Form electronic, as appropriate. Paper forms are only intended as a back-up option when the electronic system is not functioning.

- Any laboratory test result that is clinically significant or meets the definition of an SAE

- Any laboratory test result abnormality that required the participant to have study treatment discontinued or interrupted
- Any laboratory test result abnormality that required the participant to receive specific corrective therapy

It is expected that wherever possible, the clinical rather than laboratory term would be used by the reporting investigator (eg, anemia versus low hemoglobin value).

Some coagulation tests (eg, aPTT,) are affected by the investigational drug and therefore changes in such tests are not to be considered as AEs but as PD biomarkers.

9.2.7 Potential Drug Induced Liver Injury (DILI)

Wherever possible, timely confirmation of initial liver-related laboratory abnormalities should occur prior to the reporting of a potential DILI event. All occurrences of potential DILIs, meeting the defined criteria, must be reported as SAEs (see [Section 9.2](#) and [Appendix 3](#) for reporting details).

Potential drug induced liver injury is defined as:

Wherever possible, timely confirmation of initial liver-related laboratory abnormalities should occur prior to the reporting of a potential DILI event. All occurrences of potential DILIs, meeting the defined criteria, must be reported as SAEs (see [Appendix 3](#) for reporting details).

Potential drug induced liver injury is defined as:

1) AT (ALT or AST) elevation > 3 times ULN

AND

2) Total bilirubin > 2 times ULN, without initial findings of cholestasis (elevated serum alkaline phosphatase),

AND

3) No other immediately apparent possible causes of AT elevation and hyperbilirubinemia, including, but not limited to, viral hepatitis, pre-existing chronic or acute liver disease, or the administration of other drug(s) known to be hepatotoxic.

9.2.8 Other Safety Considerations

Any significant worsening noted during interim or final physical examinations, electrocardiogram, x-ray filming, any other potential safety assessment required or not required by protocol should also be recorded as a non-serious or serious AE, as appropriate, and reported accordingly.

9.3 Overdose

An overdose is defined as the accidental or intentional administration of any dose of a product that is considered both excessive and medically important. All occurrences of overdose must be reported as an SAE (see [Section 9.2](#)).

Clinical Protocol
BMS-986177

CV010010
FXIa

9.4 Safety

Planned timepoints for all safety assessments are listed in the Schedule of Activities.

9.4.1 Physical Examinations

Refer to Schedule of Activities.

9.4.2 Vital signs

Refer to Schedule of Activities.

9.4.3 Electrocardiograms

Refer to Schedule of Activities.

9.4.4 Clinical Safety Laboratory Assessments

Investigators must document their review of each laboratory safety report.
A local laboratory will perform the analyses and will provide reference ranges for these tests.

Results of clinical laboratory tests performed on Day -1 to -3 must be available prior to first dose of study drug.

Hematology	
Hemoglobin	
Hematocrit	
Total leukocyte count, including differential	
Platelet count	
Coagulation	
PT	
aPTT	
INR	
Serum Chemistry	
Aspartate aminotransferase (AST)	Total Protein
Alanine aminotransferase (ALT)	Albumin
Total bilirubin	Sodium
Direct bilirubin	Potassium
Alkaline phosphatase	Chloride
Lactate dehydrogenase (LDH)	Calcium
Creatinine	Phosphorus
Blood Urea Nitrogen (BUN)	Magnesium
Uric acid	Creatine kinase
Fasting glucose (if possible)	

Urine Dipstick
Blood (only if the participant is able to produce urine)
Serology
HIV-1 and -2 antibody (screening only)
Other Analyses
Test for drugs of abuse (urine or saliva or plasma)
Alcohol breathalyzer
Fecal occult blood (screening and after each treatment period if sample can be obtained)
Pregnancy test (urine or blood)- WOCBP only

9.4.5 Suicidal Risk Monitoring

Not Applicable

9.4.6 Imaging Safety Assessment

Not Applicable

9.5 Pharmacokinetic

Pharmacokinetics of BMS-986177 will be derived from plasma concentration versus time. The pharmacokinetic parameters to be assessed include:

C _{max}	Maximum observed plasma concentration
T _{max}	Time of maximum observed plasma concentration
AUC(0-T)	Area under the plasma concentration-time curve from time zero to time of last quantifiable concentration
AUC(INF)	Area under the plasma concentration-time curve from time zero extrapolated to infinite time
AUC(0-48)	Area under the plasma concentration-time curve from time zero to 48 hours
T-HALF	Terminal plasma half-life
f _u	Fraction of unbound drug
C _{max} f _u	Maximum observed plasma concentration of free drug
AUC(0-T)f _u	Area under the plasma concentration-time curve from time zero to time of last quantifiable concentration of free drug
AUC(INF)f _u	Area under the plasma concentration-time curve from time zero extrapolated to infinite time of free drug
AUC(3-7)	Area under the plasma concentration-time curve from 3 to 7 hours. (ie, during dialysis. Determined from blood samples entering and exiting the dialyzer)
%DR	Percent dose of BMS-986177 recovered in dialysate (%)
CLD	Dialysate clearance of drug from plasma Cumulative amount in dialysate over 3 to 7 hours postdose divided by plasma AUC(3-7)

Revised Protocol No.: 03

Date: 06-Sep-2017

40

Individual participant pharmacokinetic parameter values will be derived by non-compartmental methods by a validated pharmacokinetic analysis program. Actual times will be used for the analyses.

Table 9.5-1: Pharmacokinetic Sampling Schedule for BMS-986177

Day of Sample Collection when BMS-986177 is dosed	Event	Time Relative to BMS-986177 Dose) Hour: Min	BMS-986177 Blood Sample for PK	BMS-986177 Protein Binding Sample	BMS-986177 Dialysate Sample
BMS-986177 dosing day (depending on randomization sequence it may be study day 1, 5, 8, or 12)	predose	00:00	X ^a		
	postdose	1:00	X		
	hemodialysis start ^c	3:00	X ^b		X (3-7) ^e
		3:30	X ^b		
		4:00	X ^b		
		5:00	X ^b	X	
		6:00	X ^b		
	hemodialysis stop ^c	7:00	X ^b		
		8:00	X		
		9:00	X		
24 to 72 hours after BMS-986177 dosing		24:00 - 72:00 ^d	X		

Note: Day 1, 5, 8, and 12 is the start of Period 1, 2, 3, and 4, respectively. Hemodialysis duration could range from 3 to 4 hours but should be consistent on the days when study drug is administered.

- ^a Sample to be obtained prior to study drug administration.
- ^b Two blood samples are obtained at each of these time points (one sample is collected prior to entering the dialyzer and the second sample is collected after exiting the dialyzer) for Periods for BMS-986177 only
- ^c Sample to be collected from the blood prior to entering the dialyzer.
- ^d Single sample between days 2-4, days 6-8, days 9-11, and days 13-15.
- ^e Dialysate sample to be collected hourly between 3 to 7 hr during the hemodialysis session.

Clinical Protocol
BMS-986177

CV010010
FXIa

The plasma samples will be analyzed for BMS-986177 by a validated LC/MS/MS assay. In addition, plasma samples will be archived for potential metabolite analysis, if the need arises and to the extent possible.

Detailed instructions for the PK blood collection, labeling, processing, storage, and shipping will be provided to the site in the procedure manual.

After the scheduled PK analyses are completed, residual plasma may be used for metabolite profiling. If these analyses are conducted, they will be reported separately from the CSR.

9.6 Pharmacodynamics

Blood will be drawn at the times indicated in Table 9.6-1 and Table 9.6-2, for the measurement of pharmacodynamic markers (PD): aPTT, and Factor XI clotting activity (FXIc) for BMS-986177, aPTT and Anti-Xa for heparin and Enoxaparin. Further details of blood collection and processing will be provided to the site in the procedure manual.

Table 9.6-1: Pharmacodynamic Sampling Schedule for dialysis session with BMS-986177 and Enoxaparin

Event	Time (Relative To BMS-BMS- 986177 or Enoxaparin Dose) Hour: Min	Blood Sample for aPTT, FXIc (BMS-986177 day only) ^a	Blood Sample for aPTT and anti-Xa (Enoxaparin day only) ^a
predose	00:00	X	X
	01:00	X	X
Hemodialysis start	03:00	X ^a	X ^a
	04:00	X ^a	X ^a
	05:00	X ^a	X ^a
	06:00	X ^a	X ^a
Hemodialysis stop	07:00	X ^a	X ^a
	08:00	X	X
	09:00	X	X
24 to 72 hours after BMS-986177 dosing	24:00 - 72:00 ^b	X	

Note: Hemodialysis duration could range from 3 to 4 hours but should be consistent on the days when study drug is administered.

^a Blood sample is collected prior to entering the dialyzer.

^b Single sample between days 2-4, days 6-8, days 9-11, and days 13-15.

Table 9.6-2: Pharmacodynamic Sampling Schedule for dialysis session with UFH

Event	Time (Relative To UFH Dose) Hour: Min	Blood Sample for aPTT and anti-Xa (UFH days only)
Predose/ Hemodialysis start	00:00	X ^a
	01:00	X ^a
	02:00	X ^a
	03:00	X ^a
Hemodialysis stop	04:00	X ^a
	05:00	X
	06:00	X

Note: Hemodialysis duration could range from 3 to 4 hours but should be consistent on the days when study drug is administered.

^a Blood sample is collected prior to entering the dialyzer.

9.7 Pharmacogenomics

9.7.1 Genotyping and ADME Sampling

A 6-mL whole blood sample will be drawn at baseline for dosed participants as indicated in Section 2 Schedule of Activities) for potential analysis of DNA variants in ADME-related genes (see Appendix 5) which contains the lists of ADME-related genes from <http://pharmaadme.org>), and/or hemostasis and thrombosis related genes. Further details of blood collection and processing will be provided to the site in the procedure manual.

[REDACTED]

9.8.1 Additional Research Collection

Additional research collections and retention are mandatory for all subjects, except where prohibited by local laws or regulations.

This protocol will include residual sample storage for additional research (AR).

This collection for additional research is intended to expand the translational R&D capability at Bristol-Myers Squibb, and will support as yet undefined research aims that will advance our understanding of disease and options for treatment. It may also be used to support health authority requests for analysis, and advancement of pharmacodiagnostic development to better target drugs to the right patients. This may also include genetic/genomic exploration aimed at exploring disease pathways, progression and response to treatment etc.

All requests for access to samples or data for additional research will be vetted through a diverse committee of the study sponsor's senior leaders in Research and Development to ensure the research supports appropriate and well-defined scientific research activities.

Residual plasma from PD and biomarker collections (see Table 9.6-1, Table 9.6-2, Table 9.8-1, and Table 9.8-2) will also be retained for additional research purposes.

Samples will be securely stored by the BMS Biorepository in NJ or at a BMS approved third party storage management facility.

Samples will be stored in a coded fashion, and no researcher will have access to the key. The key is securely held by the Investigator at the clinical site, so there is no direct ability for a researcher to connect a sample to a specific individual

Additional research samples will be retained for 15 years or the maximum allowed by applicable law. No additional sampling is required for residual collections.

Further details of sample collection and processing will be provided to the site in the procedure manual.

Table 9.8.1-1: Residual Sample Retention for Additional Research Schedule

Sample Type	Timepoints for which residual samples will be retained
D-dimer, F1.2 and exploratory sample	All time points as in Table 9.8-1 and Table 9.8-2
aPTT, FXIc, anti-Xa	All time points as in Table 9.6-1 and Table 9.6-2

9.8.2 Other Assessments

Not Applicable

9.9 Health Economics OR Medical Resource Utilization and Health Economics

Health Economics/Medical Resource Utilization and Health Economics parameters will not be evaluated in this study.

10. STATISTICAL CONSIDERATIONS

10.1 Sample Size Determination

Although the number of patients is not based on statistical power considerations, administration of BMS-986177 to 32 subjects with ESRD would provide over 80% probability of observing at least one occurrence of any adverse event that would occur with incidence of 5% in the population from which the sample is drawn

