5. STUDY DESIGN

5.1 Overall Design

This study is a multicenter, cross-over, randomized, open-label trial with blinded endpoint assessment investigating safety and tolerability of single oral doses of BMS-986177 in patients with ESRD undergoing chronic stable HD three times per week. Secondary objectives are to assess BMS-986177 pharmacokinetics and hemodialysis success defined as completion of hemodialysis without premature interruption of the procedure due to complete clotting of the dialytic circuit and/or filter.

Study treatments will be administered on the first and last HD day of the week (either Monday and Friday, or Tuesday and Saturday, depending on the patients HD schedule), for a total of 4 treatment days (2 doses of BMS-986177, 1 dose of UFH, 1 dose of Enoxaparin).

The 2nd HD day of the week is not a study treatment day; on that day, study patients will undergo dialysis with standard of care, as per their schedule, and no study activities will be performed on those days.

Screening for inclusion in the study will be performed up to 28 days before the first study visit. After screening and meeting eligibility as per inclusion and exclusion criteria, patients will be randomized to 1 of following 4 sequences that will be conducted in parallel.

Sequence No.	Period			
	1	2	3	4
1	UFH	BMS dose 1 (BMS-986177 100 mg)	BMS dose 2 (BMS-986177 300 mg)	Enoxaparin
2	BMS dose 1 (BMS-986177 100 mg)	Enoxaparin	UFH	BMS dose 2 (BMS-986177 300 mg)
3	BMS dose 2 (BMS-986177 300 mg)	UFH	Enoxaparin	BMS dose 1 (BMS-986177 100 mg)
4	Enoxaparin	BMS dose 2 (BMS-986177 300 mg)	BMS dose 1 (BMS-986177 100 mg)	UFH

Note: Per amendment/revised protocol 01, the BMS-986177 doses will be 100 mg (BMS dose 1) and 300 mg (BMS dose 2).

Clinical Protocol
BMS-986177

CV010010
FXIa

Study patients will be admitted to the study facility the same day of HD treatment day or the night before. Assessment of vital signs and clinical biochemistry will be performed pre-dose.

Study treatments will be administered:

- BMS-986177: one single oral dose 3 hours prior beginning the HD session
- UFH: I.V. infusion to start within 10 minutes prior beginning the HD session. The dosage and duration of UFH use are at the discretion of the physicians and are per their institutional practice.
- Enoxaparin: one single dose (40 mg) by subcutaneous injection 3 hours prior beginning the HD session

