The HD session will last approximately 4 hours. However, the duration could range from 3 to 4 hours but should be consistent on the days when study drug is administered. After the HD, patients will remain in the study facility for at least:

- Approximately 3 hours post-HD on UFH and Enoxaparin treatment days
- Approximately 24 hours post-dose on BMS-986177 days

Site staff members blinded to treatment will perform an assessment of clot formation according to criteria set forth in the Clot Formation Assessment Manual which will be provided to the site in a separate document.

Physical examinations, vital sign measurements, 12-lead electrocardiograms (ECG), and clinical laboratory evaluations will be performed at selected times throughout the dosing interval. Participants will be closely monitored for adverse events throughout the study. Blood samples will be collected for up to 72 hours after study drug administration for pharmacokinetic (PK) analysis and pharmacodynamic (PD) analysis. Approximately 365 mL of blood will be drawn from each participant during the study.

The study design schematic is presented in Figure 5.1-1.

Figure 5.1-1: Study Design Schematic

		Week 1							Week 2						
Days	D-21 to D-1	D1*	D2	D3	D4	D5 [†]	D6	D7	D8*	D9	D10	D11	D12 [†]	D13 to D15	
HD days		1 st HD		2 nd HD		3 rd HD			1 st HD		2 nd HD		3 rd HD		
Study activity	S - E - R	Tx				Tx			Tx				Tx	D	

HD = Hemodialysis session. S= Screening. E = Enrollment. R = Randomization. Tx = Study treatment day (BMS-986177 dose 1 or dose 2, or unfractionated heparin, or enoxaparin). D = Study discharge.

* D1 and D8 can be Monday or Tuesday depending on the patient's dialysis schedule.

† D5 and D12 can be Friday or Saturday depending on the patient's dialysis schedule.

Clinical Protocol
BMS-986177

CV010010
FXIa

Note: Per amendment/revised protocol 01, the BMS-986177 doses will be 100 mg (BMS dose 1) and 300 mg (BMS dose 2).

5.1.1 *Data Monitoring Committee and Other External Committees*

Not Applicable

5.2 **Number of Participants**

Target sample size is 32 participants to achieve 24 participants who completed the 4 study treatments.

5.3 **End of Study Definition**

[figure not shown]

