## 2.2 Treatment Assignment

Study treatment will be dispensed at the study visits Days 1, 5, 8, and 12.

Enrolled participants, including those not dosed, will be assigned sequential participant numbers starting with 00001, (eg, 00001, 00002, 00003.... 00010). Sequential numbering may restart at 00001 for each participating site as the distinct patient identification number will ultimately be comprised of the site number and participant number, (eg, 0002 00001). Those enrolled participants meeting inclusion and exclusion criteria will be eligible to be randomized.

Eligible patients will be randomly assigned to 1 of the 4 sequences as listed in Table 2.1-1 in 1:1:1:1 ratio according to a computer-generated randomization scheme. Randomization numbers will be assigned prior to dosing.

Participants will not be replaced if they are discontinued from the study secondary to an AE unless the AE can be determined to be unrelated to treatment. If a participant is replaced after dosing, then the replacement participant will be assigned the original participant's number plus 100. The replacement participant will receive the same treatment as the participant being replaced but a new randomization number will be assigned to him or her. For example, participant 4 would be replaced by Participant 104.

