## 5 SAMPLE SIZE AND POWER

Although the number of patients is not based on statistical power considerations, administration of BMS-986177 to 32 patients with ESRD would provide over 80% probability of observing at

least one occurrence of any AE that would occur with incidence of 5% in the population from which the sample is drawn.

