##### **7.6.3 Adverse Events**

Adverse events which occur on or after the first dose of study treatment will be tabulated. Events will be assigned to the last study treatment administered at the time of onset. Events occurring after discharge will be assigned to the last study treatment received. The proportion of patients having an AE will be calculated as the number of patients having the event in the specific treatment interval, divided by the total number of patients receiving study treatment during that treatment interval.

All AE listings will indicate the unique patient identifier, age, gender, current treatment, date of onset, date of resolution, day of onset relative to the start of treatment, action taken, investigator's assessment of severity, and relationship to study treatment. Additional listings will be provided for AEs leading to discontinuation and AEs without recorded resolution.

All AEs will be summarized by system organ class (SOC), preferred term (PT), treatment, and overall for the safety population. Summaries of AEs will include AEs, AEs by intensity, AEs related to study treatment, and AEs leading to discontinuation.

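### Does the chance of over 80% of seeing a 5% adverse event with 32 patients need restating for each BMS-986177 dose?

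*Protocol*

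**What the plan says.** Protocol 10.1 opens with the qualifier "Although the number of patients is not based on statistical power considerations" and then gives one figure: "administration of BMS-986177 to 32 subjects with ESRD would provide over 80% probability of observing at least one occurrence of any adverse event", for events with a 5% incidence in the source population. SAP 5 repeats both parts, with "administration of BMS-986177 to 32 patients with ESRD would provide over 80% probability".

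The rest of the design bears on how that figure is read:

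- Protocol 5.1 gives each patient four treatment days ("2 doses of BMS-986177, 1 dose of UFH, 1 dose of Enoxaparin"). The two BMS-986177 doses are 100 mg and 300 mg.
- Protocol 5.2: "Target sample size is 32 participants to achieve 24 participants who completed the 4 study treatments".
- SAP 2.2 allocates patients to the four sequences "in 1:1:1:1 ratio according to a computer-generated randomization scheme".
- SAP 7.6.3: "All AEs will be summarized by system organ class (SOC), preferred term (PT), treatment, and overall for the safety population". The denominator for each proportion is the number with the event "divided by the total number of patients receiving study treatment during that treatment interval".
- SAP 6.2 lists the two BMS-986177 doses as separate treatments, B and C.

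**The concern.** The sentence speaks of giving BMS-986177 to 32 patients without saying whether that means at least one dose or each dose. The adverse-event tables have a column per dose, so a reader could carry the figure across to the 100 mg or 300 mg column. It has no slack: 32 is the smallest number that exceeds 80%. Protocol 5.2 also allows for 32 - 24 = 8 patients not completing all four treatments. Every non-completer misses Period 4, and for two of the four sequences Period 4 is a BMS-986177 dose.

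This is the only quantitative statement attached to the sample size, and safety is the primary objective. If it were taken as a per-dose assurance, the absence of an event in one dose column would look somewhat more reassuring than it is. A related worry is that the only combined summary SAP 7.6.3 names is the overall one, which also takes in UFH and enoxaparin.

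**Working it through.** **The plan's own figure.** Inputs: n = 32 and incidence 5% per patient (Protocol 10.1). The probability of at least one event is 1 - (1 - 0.05)^n.

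- n = 32: 1 - 0.95^32 = 0.8063, or 80.6%. The stated figure is reproduced.
- n = 31: 1 - 0.95^31 = 0.7961, or 79.6%. So 32 is the smallest n above 80%.

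**Exposure by sequence** (sequence table in Protocol 5.1; eight patients per sequence from 32 allocated equally):

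| Sequence | 100 mg given in | 300 mg given in | First BMS-986177 dose |
|---|---|---|---|
| 1 | Period 2 | Period 3 | Period 2 |
| 2 | Period 1 | Period 4 | Period 1 |
| 3 | Period 4 | Period 1 | Period 1 |
| 4 | Period 3 | Period 2 | Period 2 |

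Every sequence reaches a first BMS-986177 dose by Period 2. The 300 mg dose in sequence 2 and the 100 mg dose in sequence 3 come only in Period 4.

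**Dropout of 8, two per sequence, no replacement, no stopped arm.** The even split is an assumption; the documents give neither the timing nor the pattern of dropout.

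| All 8 leave after | Exposed to each dose | 1 - 0.95^n | Exposed to any dose | 1 - 0.95^n |
|---|---|---|---|---|
| Period 1 | 32 - 6 = 26 | 73.6% | 32 - 4 = 28 | 76.2% |
| Period 2 | 32 - 4 = 28 | 76.2% | 32 | 80.6% |
| Period 3 | 32 - 2 = 30 | 78.5% | 32 | 80.6% |

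Under this pattern the per-dose figure cannot exceed 78.5%.

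**Without the even split.** If all 8 leave after Period 3 from sequences 1 and 4, both doses still reach 32 (80.6%). If all 8 come from sequence 2, 300 mg falls to 32 - 8 = 24 (70.8%); if all 8 come from sequence 3, the same happens to 100 mg. Dropout before any dosing gives 24 on either reading. The bounds are therefore 24 to 32 exposed, 70.8% to 80.6%, whichever reading is taken.

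**Outside those assumptions.** Protocol 7.2 permits some replacement, and Protocol 10.2 counts replacements among the randomized; 33 exposed would give 81.6%. Protocol 8.1 allows a BMS-986177 arm to be stopped and replaced by UFH, which would lower exposure to that dose; purely as an illustration, 20 exposed would give 64.2%.

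**The case for a change.** The best case for a change is that the wording is incomplete where it matters and the repair is cheap. The figure has no margin, and the per-dose reading falls below 80% under evenly spread dropout whatever its timing. The any-dose reading, the one that makes the sentence true, has no matching table named in SAP 7.6.3. The overall column mixes in UFH and enoxaparin. The two dose columns cannot be added to give a patient-level incidence, because one patient can count in both.

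The arithmetic in that case stands, and so does the observation that the sentence does not literally say any dose. The rest carries less weight:

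- **The reading.** The sentence names the drug and no dose level, and the primary objective is also framed for the drug. At least one dose is the ordinary reading. A per-dose claim has to be brought in from the table layout; neither sample-size section makes one.
- **The lower figures.** Each replaces the stated premise, 32 patients given the drug, with a smaller number. The 78.5% ceiling further needs two dropouts per sequence and no replacement, neither of which the documents state. The 8 is an allowance implied by two targets, not a forecast.
- **The missing column.** SAP 7.6.3 plans adverse-event listings by patient with the current treatment, and SAP 7.4 lists treatment administration. Patients with an event on either dose, and patients given at least one dose, can both be counted once from these. If neither dose column shows an event, the any-dose count is zero as well. SAP 8 puts table detail in a Data Presentation Plan that is not among the documents, so an omission cannot be established.

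**Conclusion.** The stated figure is correct: 80.6% if 32 patients receive at least one BMS-986177 dose, with 5% taken as a per-patient incidence. It should not be read as a property of the 100 mg or 300 mg column alone. There, with 8 non-completers, no replacement and no stopped arm, the probability lies between 70.8% and 80.6%, and is at most 78.5% if dropout is two per sequence.

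That gap does not call for an amendment. The best evenly spread case is about 1.5 points under 80% (80 - 78.5), the number of patients is expressly not chosen for power, no hypothesis is tested, and nothing in the conduct or analysis turns on passing 80%. Spelling out the exposure in the sentence would be harmless, but it would alter neither enrolment nor any planned result. A statistician writing the report will quote the probability for the number actually exposed, overall or by dose, and can tabulate any-dose events from data already planned for listing.
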